###### **7.1.1.1.1 General Informed Consent**

Consent given by the subject's legally acceptable representative must be documented on a consent form.

A copy of the signed and dated consent form should be given to the subject's legally acceptable representative before that subject's participation in the trial.

The initial informed consent form, any subsequent revised informed consent form and any written information provided to the subject's legally acceptable representative must receive the IRB/ERC's approval/favorable opinion in advance of use. The subject's legally acceptable representative should be informed in a timely manner if new information becomes available that may be relevant to willingness for the subject to continue participation in the trial. The communication of this information will be provided and documented via a revised consent form or addendum to the original consent form that captures the subject's legally acceptable representative's dated signature.

Specifics about a trial and the trial population will be added to the consent form template at the protocol level.

The informed consent will adhere to IRB/ERC requirements, applicable laws and regulations and Sponsor requirements.

### **7.1.1.2 Inclusion/Exclusion Criteria**

All inclusion and exclusion criteria will be reviewed by the investigator or qualified designee to ensure that the subject qualifies for the trial.

### **7.1.1.3 Subject Identification Card**

The legally acceptable representative for each subject will be given a Subject Identification Card identifying the subject as a participant in a research trial. The card will contain trial site contact information (including direct telephone numbers) to be utilized in the event of an emergency. The investigator or qualified designee will provide the legally acceptable representative for each subject with a Subject Identification Card immediately after documented informed consent is provided. At the time of treatment allocation/randomization, site personnel will add the treatment/randomization number to the Subject Identification Card.

The subject identification card also contains contact information for the emergency unblinding call center so that a health care provider can obtain information about trial medication/vaccination in emergency situations where the investigator is not available.

### **7.1.1.4 Medical History**

A medical history will be obtained by the Investigator or qualified designee.

### **7.1.1.5 Prior and Concomitant Medications Review**

#### **7.1.1.5.1 Prior Medications**

The Investigator or qualified designee will review prior medication use, including any protocol-specified washout requirement, and record prior medication taken by the subject within 30 days before first dose of trial medication.

#### **7.1.1.5.2 Concomitant Medications**

The Investigator or qualified designee will record medication, if any, taken by the subject during the trial.

### **7.1.1.6 Assignment of Screening Number**

All consented subjects will be given a unique screening number that will be used to identify the subject for all procedures that occur prior to randomization or treatment allocation. Each subject will be assigned only one screening number. Screening numbers must not be re-used for different subjects.

Any subject who is screened multiple times will retain the original screening number assigned at the initial screening visit.

Specific details on the Screening Visit requirements (screening/rescreening) are provided in Section 7.1.5.1.

### **7.1.1.7 Assignment of Treatment/Randomization Number**

All eligible subjects will be allocated, by non-random assignment, and will receive a treatment/randomization number. The treatment/randomization number identifies the subject for all procedures occurring after treatment allocation/randomization. This will occur after consent is obtained, and confirmation of study eligibility (Section 5.3). Once a treatment/randomization number is assigned to a subject, it can never be re-assigned to another subject.

A single subject cannot be assigned more than 1 treatment/randomization number.

### **7.1.1.8 Trial Compliance**

Interruptions from the protocol-specified procedures require consultation between the investigator and the Sponsor and written documentation of the collaborative decision on subject management.

Administration of each dose of trial medication will be witnessed by the investigator and/or trial staff and the time and date will be recorded in the Subject's e-CRF.

## **7.1.2 Clinical Procedures/Assessments**

### **7.1.2.1 Physical Examination**

Physical examinations will be conducted as per the trial flowchart. All physical examinations will include height and weight (at Screening), and vital signs (blood pressure [BP], heart rate [HR], respiratory rate, and temperature [oral, tympanic, temporal, or rectal]).

Note: a consistent method should be used to obtain body temperature, and the subject should be in the same resting position for all vital sign measurements.

### **7.1.2.2 Electrocardiogram**

A local ECG (minimal 5-lead ECG) will be required at screening\*. A prestudy ECG may be used if it was performed and documented within 1 month prior to enrollment.

\*ECG is not required for neonates, but available ECG data should be reviewed.

## **7.1.3 Laboratory Procedures/Assessments**

Details regarding specific laboratory procedures/assessments to be performed in this trial are provided below. The total amount of blood/tissue to be drawn/collected over the course of the trial (from pretrial to post-trial visits), including approximate blood/tissue volumes drawn/collected by visit and by sample type per subject can be found in the Laboratory Manual.

### **7.1.3.1 Laboratory Safety Evaluations (Hematology, Chemistry and Urinalysis)**

Laboratory tests for hematology, chemistry and urinalysis are specified in [Table 3](#).

Table 3 Laboratory Tests

Hematology	Chemistry	Urinalysis
Hematocrit	Albumin	Blood
Hemoglobin	Alkaline phosphatase	Glucose
Platelet count	Alanine aminotransferase (ALT)	Protein
WBC (total and differential)	Aspartate aminotransferase (AST)	Specific gravity
Neutrophils (%, absolute)	Bicarbonate	Microscopic examination, if abnormal results are noted
Lymphocytes (%, absolute)	Calcium	pH
Monocytes (%, absolute)	Chloride	Bilirubin
Eosinophils (%, absolute)	Cholesterol a	Ketones
Basophils (%, absolute)	Creatinine	Urobilinogen
Bands (%, absolute)	Gamma-glutamyl transpeptidase a	
	Glucose	
	Phosphorus a	
	Potassium	
	Sodium	
	Total bilirubin	
	Direct bilirubin, if total bilirubin is elevated above the upper limit of normal	
	Indirect bilirubin a	
	Total protein	
	Uric acid a	
	Blood urea nitrogen	

WBC=white blood cell

a Not required, but will be collected if analyzed per local standard of care.

#### 7.1.3.2.2 Samples

In Part A, blood samples for analysis of tedizolid phosphate and tedizolid will be collected at the following timepoints ([Figure 2](#) or [Figure 3](#)) for subjects allocated to 1 of 2 collection schemes:

Subjects who receive single-dose tedizolid phosphate IV (shown graphically in [Figure 2](#)):

1. immediately after the end of the 1-hour infusion, and at 3 and 12 hours after the start of infusion

OR

2. at 1.5, 6, and 24 hours after the start of infusion

Subjects who receive multiple-dose tedizolid phosphate IV (shown graphically in [Figure 3](#)):

1. Day 3 at end of infusion (5th dose), 3 hours after the start of the 5th infusion, and 12 hours after the start of the 5th infusion (prior to 6th dose)

OR

2. Day 3 at 12 hours after the start of the 4th infusion (prior to 5th dose), 1.5 hours after the start of the 5th infusion, and 6 hours after the start of the 5th infusion

In Part B, blood samples for analysis of tedizolid phosphate and tedizolid will be collected at the following timepoints ([Figure 4](#)) for subjects allocated to 1 of 2 collection schemes:

Subjects who receive single-dose tedizolid phosphate oral suspension (shown graphically in [Figure 4](#)):

[figure not shown]
1. at 1, 5, and 12 hours postdose

OR

2. at 3, 8, and 24 hours postdose

[figure not shown]
[Figure 2](#), [Figure 3](#), and [Figure 4](#) provide the allowed windows for collection of blood samples.

Figure 2 Pharmacokinetic Sampling Schemes for Subjects Who Receive Single-dose Tedizolid Phosphate IV

[figure not shown]
h=hour; IV=intravenous; min=minute(s); PK=pharmacokinetics

Figure 3 Pharmacokinetic Sampling Schemes for Subjects Who Receive Multiple-dose Tedizolid Phosphate

h=hour; IV=intravenous; min=minute(s); PK=pharmacokinetics

Figure 4 Pharmacokinetic Sampling Schemes for Subjects Who Receive Single-dose Tedizolid Phosphate Oral Suspension

h=hour; min=minutes; PK=pharmacokinetics; PO=oral

Note: PK samples will not be collected from subjects receiving oral suspension who vomit during and/or within 90 minutes after administration of a dose.

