After dose adjustment based on the first interim assessment, Group 1 Cohorts 1 and 2 will continue enrolling until complete; then Group 4 (aged 28 days to <2 years, receiving oral suspension) will enroll. In parallel, the first cohorts of Groups 2 and 3 (single-dose IV, full-term and preterm neonatal age groups) will begin enrollment at the planned starting dose of 3.0 mg/kg (body weight <10 kg) or 2.5 mg/kg (body weight 10 to <30 kg). After 6 subjects each are enrolled in the first cohorts of Groups 2 and 3, separate interim assessments will be performed for a potential dose adjustment. Enrollment of the second cohorts of Groups 2 and 3 (multiple-dose tedizolid phosphate) will occur only after these separate interim assessments.

Note, as of Amendment 05, these assessments have been completed, and enrollment of the second cohorts of Groups 2 and 3 (multiple-dose IV, full-term and preterm neonatal groups) will be initiated, supported by the safety profile observed across all age groups in studies MK-1986-014 and MK-1986-018.

Along with the second cohorts of Groups 2 and 3, Groups 5 and 6 will open for enrollment. Given the high bioavailability of tedizolid (approximately 90%) expected based on data from adults and older children, the oral suspension treatment will be administered at the dose selected based on the interim IV PK data. No interim analyses are planned for Part B (oral suspension) because of the small size of the oral groups.

Each of the IV groups (Group 1 [Cohorts 1 and 2 combined], Group 2 [Cohorts 1 and 2 combined], and Group 3 [Cohorts 1 and 2 combined]) will contain at least 10 subjects, with interleaved PK sampling such that data from all timepoints are obtained but no single subject provides more than 3 PK samples, to ensure total blood collection volume is within a safe range for the age group. Similarly, the oral groups (Groups 4, 5, and 6) will each have at least 4 subjects, again with interleaved PK sampling. Because of the relatively sparse nature of the sampling, subjects may be replaced if they are missing >1 PK sample (see Section 5.9).

[figure not shown]
Further local restrictions on cohort opening may be applied based on country-specific requirements or site constraints.

Specific procedures to be performed during the trial, as well as their prescribed times and associated visit windows, are outlined in the Trial Flow Chart - Section 6.0. Details of each procedure are provided in Section 7.0 – Trial Procedures.

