#### **4.1.1 Pharmaceutical and Therapeutic Background**

Tedizolid phosphate (SIVEXTRO®, MK-1986) is a novel oxazolidinone prodrug antibiotic that is rapidly converted in vivo by phosphatases to the microbiologically active moiety tedizolid. Tedizolid is a protein synthesis inhibitor that interacts with the 50S subunit of the bacterial ribosome. Tedizolid has bacteriostatic activity against gram-positive bacteria including common skin pathogens *Staphylococcus aureus* (both methicillin-sensitive and –resistant strains) and *Streptococcus pyogenes*, less common species causing acute bacterial skin and skin structure infections (ABSSSI), *S. anginosus*-milleri group and *Enterococcus faecalis*, and other gram-positive aerobes and anaerobes. The tablet is highly (~90%) bioavailable after oral dosing in adults, and is provided in both IV and oral formulations. Following oral administration of a single 200 mg dose to healthy adults, maximal plasma concentrations of tedizolid (approximately 2 µg/mL) are achieved approximately 3 hours after dosing when fasted; Tmax is delayed by approximately 6 hours when tedizolid phosphate is dosed with a meal; however, the AUC is unaffected by administration with or without food. Conversion of the prodrug tedizolid phosphate to the active metabolite, tedizolid, is extremely rapid, with a half-life of 10 minutes. When the drug is dosed IV, exposure peaks at the end of the 60-minute infusion period. Systemic prodrug is rarely detectable after oral dosing. The terminal half-life of tedizolid elimination is 12 hours. Exposure is generally dose-proportional in humans.

Tedizolid phosphate is approved for the treatment of ABSSSI in adults in multiple regions, including the United States and European Union (EU), but its safety and effectiveness have not been established in children and adolescents.

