#### **5.2.1.1.2 Oral Tedizolid Phosphate**

Oral tedizolid phosphate may be administered with or without food, but timeframe of the most recent meal must be recorded.

The target dose for administration of the oral suspension is based on body weight using the following formula:

$$\text{Target dose (mg/kg)} \times \text{body weight (kg)} = \text{dose required (mg)}$$

$$\text{Dose required (mg)} / \text{suspension concentration (mg/mL)} = \text{target volume (mL)}$$

Calculations of volume required are provided in the Pharmacy Manual.

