### 8.2.3 Approaches to Analyses

The following populations are defined for the analysis and reporting of data. All subjects will be reported, and their data analyzed, according to the treatment(s) they actually received.

*All Subjects as Treated (ASaT)* - All subjects who received at least one dose of the investigational drug. This population will be used for assessments of safety and tolerability.

*Per-Protocol (PP)* – The set of data generated by the subset of subjects who comply with the protocol sufficiently to ensure that these data will be likely to exhibit the effects of treatment, according to the underlying scientific model. Compliance covers such considerations as exposure to treatment, availability of measurements and absence of important protocol deviations. Important protocol deviations will be identified to the extent possible by individuals responsible for data collection/compliance, and its analysis and interpretation. Any subjects or data values excluded from analysis will be identified, along with their reason for exclusion, in the CSR. At the end of the study, all subjects who are compliant with the study procedure as aforementioned and have valid samples collected for at least 2 of the assigned 3 time points will be included in the primary analysis dataset. This population will be used for the PK analyses.

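### Vomiting later than 90 minutes after an oral dose, but before the stated Tmax, has no prespecified PK handling and can distort the pooled oral AUC and bioavailability

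*Combined protocol and SAP*

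**What the plan says.** Section 7.1.3.2.2, and footnote i of the flow chart in Section 6.0, give the only timed rule on lost oral dose: "PK samples will not be collected from subjects receiving oral suspension who vomit during and/or within 90 minutes after administration of a dose".

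Section 4.1.1 gives the adult kinetics. Peak tedizolid concentrations "are achieved approximately 3 hours after dosing when fasted", "Tmax is delayed by approximately 6 hours when tedizolid phosphate is dosed with a meal", and "The terminal half-life of tedizolid elimination is 12 hours". Section 5.2.1.1.2 allows fed dosing: "Oral tedizolid phosphate may be administered with or without food, but timeframe of the most recent meal must be recorded".

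Each oral group has at least 4 infants (Section 2.1), split over two schemes: 1, 5 and 12 h, or 3, 8 and 24 h. Section 7.1.3.2.1 allows only naïve pooling for these groups: concentrations are averaged at each timepoint and one profile gives one AUC. For the PK population, Section 8.2.3 says that compliant subjects who "have valid samples collected for at least 2 of the assigned 3 time points will be included in the primary analysis dataset". It lists exposure to treatment among the compliance considerations and does not mention vomiting. Neither does Section 8.2.4.3.

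Two other texts bear on the point. Section 7.1.5.3 says that infants who spit up the oral dose do not need PK sampling, with no time limit. Section 5.9 allows replacement when a subject discontinues from the trial or is missing more than one PK sample.

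**The concern.** The 90-minute limit protects the oral data only while it covers the period in which much of the dose could still be expelled. By the protocol's own figures absorption continues well past it, above all after a meal. An infant who vomits at 2 h does so before all three scheme 2 samples and before two of the three scheme 1 samples. That infant breaches no stated procedure and satisfies the two-of-three rule. The concentrations are then averaged with about one other infant's, as if the full dose had been retained.

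Single-dose oral PK is a primary objective (Section 3.1, Part B), and each group yields a single AUC. No interim analysis covers Part B. The oral dose level follows the IV level on the stated expectation: "Given the high bioavailability of tedizolid (approximately 90%) expected based on data from adults and older children". One affected infant could therefore noticeably change a group's reported exposure and bioavailability. Nothing in the plan would make that visible, since no text requires the clock time of a vomit. Table 5 asks for adverse event dates, and a duration if under a day.

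**Working it through.** **Cut-off against Tmax** (Section 4.1.1)
- Fasted: 1.5 h / 3 h = 0.50, so exactly half of the stated approximate value.
- Fed, delayed *by* 6 h: 1.5 / (3 + 6) = 0.17. Fed, if read as delayed *to* 6 h: 1.5 / 6 = 0.25.

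**Model (illustration only).** One compartment with first-order absorption from time zero. The adult half-life of 12 h gives ke = ln 2 / 12 = 0.0578 per h. ka is solved from Tmax = ln(ka/ke)/(ka − ke). The share of dose unabsorbed at time t is exp(−ka·t).

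| Tmax | ka (per h) | Unabsorbed at 1.5 h | at 2 h | at 3 h |
|---|---|---|---|---|
| 3 h | 1.012 | 22% | 13% | 5% |
| 6 h | 0.365 | 58% | 48% | 33% |
| 9 h | 0.190 | 75% | 68% | 56% |

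**Effect on pooled AUC0-24.** Assume four infants, two per scheme, no between-subject variability, and one vomit at 2 h that expels 50% or 100% of the unabsorbed drug. Means at 0, 1, 3, 5, 8, 12 and 24 h are integrated by the plan's linear-up/log-down rule. As a rough check, the loss should be near one quarter of the unabsorbed share. For complete loss that is 0.132/4 = 3.3%, 0.482/4 = 12.0% and 0.684/4 = 17.1%.

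| Tmax | Change in pooled AUC0-24 | Oral/IV ratio, true 0.90 | IV/oral ratio, true 1.11 |
|---|---|---|---|
| 3 h | −2% to −3% | 0.89 to 0.87 | 1.13 to 1.15 |
| 6 h | −6% to −12% | 0.85 to 0.79 | 1.18 to 1.27 |
| 9 h | −8% to −17% | 0.83 to 0.75 | 1.21 to 1.34 |

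Both ratios are shown because Section 7.1.3.2.1 defines bioavailability as IV over oral and Section 8.2.4.3 as oral over IV.

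**Effect on AUC0-inf.** Section 8.2.2 defines percent bioavailability on AUC0-inf, which needs a terminal slope. The plan does not say how the slope is fitted, so two versions were run: the 12 and 24 h means, and a log-linear fit to the 8, 12 and 24 h means. AUC0-inf is AUC0-24 plus the 24 h mean divided by the slope.

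| Vomiter's scheme | Slope points | Tmax 3 h | Tmax 6 h | Tmax 9 h |
|---|---|---|---|---|
| 1 (1, 5, 12 h) | 12, 24 h | +0.3% to +0.9% | +4% to +18% | +22% or more; unstable |
| 1 | 8, 12, 24 h | −0.9% to −1.7% | −2% to −4% | +1% to +5% |
| 2 (3, 8, 24 h) | 12, 24 h | −3.5% to −7% | −13% to −24% | −23% to −38% |
| 2 | 8, 12, 24 h | −2.5% to −5% | −10% to −19% | −18% to −34% |

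A scheme 1 vomiter lowers the 12 h mean but not the 24 h mean. The terminal slope flattens and the extrapolated area grows. At Tmax 9 h with complete loss, the two-point slope drops from 0.042 to 0.006 per h, which is why that cell is called unstable. A scheme 2 vomiter lowers the 24 h mean, and both parts of the area shrink.

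**The case against.** The strongest reply is that the plan already has the means to deal with such an infant. The PK population depends on judged compliance, including exposure to treatment, and exclusions must be reported with reasons in the study report. The spit-up text in 7.1.5.3 has no time limit. A reader might infer that a late vomiter necessarily enters the pooled profile; the documents do not say so. What stands against the reply is that neither text requires exclusion. The spit-up text waives collection and is silent on samples already taken. The decision would be a case-by-case judgement in an open-label trial, where concentrations may already be known.

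A reader might also infer that oral exposure and bioavailability would always be biased low. That does not hold. AUC0-24 falls in this model, but AUC0-inf can rise when the vomiter is in scheme 1, and the IV/oral ratio in 7.1.3.2.1 moves opposite to the oral/IV ratio.

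The magnitude is open to fair attack. Adult Tmax and half-life are applied to infants and neonates. Drug already past the stomach need not be lost, so 50-100% is an upper range. No vomiting frequency is given. The fasted effect is small beside sampling error: taking the plan's SD of 0.32 for log tedizolid AUC (Section 8.2.7), a rough standard error for four subjects is 0.32/√4 = 0.16, about 16%. All of this stands, and it confines the practical concern mainly to fed dosing.

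Finally, bioavailability is exploratory, and no text says it decides whether the IV dose level carries over to the suspension. That link is inference. The oral AUC itself is nevertheless a primary result.

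**Conclusion.** The point holds as a gap in prespecification with a possible distortion behind it. The timed rule stops at half of the quoted fasted Tmax and at 17-25% of the fed Tmax. Later vomiting has no stated handling in the PK set, and the timed vomiting rule and the untimed spit-up waiver do not agree.

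With one vomit at 2 h among four infants, the change in pooled AUC0-24 is minor at Tmax 3 h (2-3%) and material at the fed values (6-12% or 8-17%). These figures rest on adult kinetics, a one-compartment model, an even split over schemes and a high assumed loss; groups larger than four would dilute them. For AUC0-inf, even the sign depends on the vomiter's scheme and the slope fit. The documents do not support a stronger claim of certain inclusion or consistent downward bias.

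**What to change.** 1. Record the clock time of every vomit up to the last PK sample, and keep sampling infants who vomit after 90 minutes.
2. In Sections 8.2.3 and 8.2.4.3, prespecify that oral AUC and bioavailability are reported twice: with all per-protocol subjects, and without those who vomit after 90 minutes but before the quoted Tmax for their fed or fasted state. State which fed Tmax is meant and how the recorded meal time defines fed. State also how the terminal slope of the pooled profile is fitted.
3. Reconcile the 90-minute rule in 7.1.3.2.2 with the spit-up text in 7.1.5.3, and the opposite bioavailability ratios in 7.1.3.2.1 and 8.2.4.3.
4. If these infants are to be replaceable, amend Section 5.9. A reader might assume it already covers them, but a late vomiter who stays in the trial and gives all samples meets neither of its conditions.

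The cost is one case report form field, a short SAP paragraph and the text reconciliation. No data are discarded. The drawback is that, without a replacement, the restricted estimate may rest on three infants, with a single infant at three of the timepoints.
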